Appendix C: Sample Size, Power, and Detectable Effects	
Appendix D: Statistical Analysis Policy	121

I. PURPOSE AND OVERVIEW OF REACT

A. Study Goal

The goal of REACT (Rapid Early Action for Coronary Treatment) is to reduce patient delay time from onset of acute myocardial infarction (AMI) symptoms to contact with hospital-based emergency medical care. To accomplish this goal, REACT will implement a community-wide intervention program and evaluate its effects on delay time. REACT will also evaluate the impact of the program on medical care, utilization of emergency medical services, and AMI associated outcomes.

REACT is a four-year multi-center randomized controlled community trial in which 10 communities will receive a community-wide intervention program and 10 matched communities will serve as a comparison group. The study is a collaborative effort between five Field Centers, a Coordinating Center, and the National Heart, Lung, and Blood Institute.

B. Study Specific Aims and Other Objectives

The primary aim of REACT is to evaluate the effect of an 18-month community-wide intervention program on patient delay time from onset of symptoms suggestive of AMI to arrival at the hospital in patients admitted for possible acute cardiac ischemia and receiving a cardiac-related discharge diagnosis.

The secondary aims of REACT are to:

- 1. develop, implement, and evaluate the implementation of an 18 month multicomponent community intervention program based on sound behavior change theory and consisting of four components: community organization, community education, professional education, and patient education.
- 2. evaluate the impact of the intervention program on factors hypothesized to be important influences on patient delay, including knowledge, attitudes, and skills of adult citizens, health care professionals, and patients about the symptoms of AMI, appropriate actions to be taken, and specific skills necessary for taking action at the time of acute symptom onset.
- 3. evaluate the effect of the intervention program on delay time from onset of AMI symptoms to arrival at the hospital (ED) in patients with AMI symptoms, including patients presenting to the Emergency Department (ED) with chest pain/discomfort, patients admitted for possible acute cardiac ischemia (rule-out MI, unstable angina, chest discomfort (or synonym)) and patients receiving 410/411 discharge diagnoses.

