The community intervention program is comprised of four interrelated components: community organization, professional education, patient education, and community education. Evaluation of the implementation of each of these four components is termed process evaluation. Process evaluation also includes assessment of similar educational programs in the control communities. Each of the four education components has specific objectives to be met as a result of intervention. Measurement and evaluation of those objectives is termed impact evaluation.

The primary outcome is delay time, defined as the time interval from onset of symptoms to hospital arrival in patients with confirmed acute cardiac ischemia (validated AMI or unstable angina). It is hypothesized that the intervention program will decrease this patient delay time. Delay time in other groups also will be examined. If the intervention is successful, utilization of the medical care system (911/EMS use, ED visits, and hospital admissions) will increase in patients with AMI symptoms.

As a result of a decrease in delay time in patients with acute cardiac ischemia, use of thrombolytic and other artery-opening and coronary reperfusion treatments should increase, and the time from symptom onset to definitive treatment should decrease. This should result in decreases in AMI severity and AMI in-hospital case fatality rates.

Major potential confounders and effect modifiers are also shown in Figure 2. Confounders are factors that we want to assure are comparable between the intervention and control communities because of previously seen associations with patient delay time. Pair-matching and randomization of communities will aid in the control of potential confounders and their measurement will allow for adjustment to control for residual confounding. Effect modifiers are factors that we hypothesize may influence the effect of the intervention program. Their measurement will enable assessment of intervention effects in subgroups defined by these factors.

REACT STUDY TIMELINE

Figure 2

REACT Framework of Intervention Process, Impact and Outcomes

II. BACKGROUND AND RATIONALE FOR THE STUDY

A. Magnitude of Coronary Heart Disease Mortality and Morbidity

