All of the study investigators have extensive experience recruiting and maintaining hospital participation in large-scale studies and will take all possible measures to prevent attrition from occurring (including periodic hospital visits for updates and feedback). We will work with the individual hospitals to anticipate and respond promptly to any unforeseen challenges that might arise. Hospital administrators are typically "good citizens" and support this type of altruistic endeavor as consistent with and supportive of the hospital's mission. The visible support of other community leaders and organizations will serve to reinforce continued hospital participation.

E. Case Inclusion Criteria

Patients will be eligible for inclusion in this study who meet the following criteria:

- 1. Age \geq 30 years (acute cardiac ischemia is uncommon at younger ages),
- 2. Residence within one of the study communities as defined by zip code of residence,
- 3. Not institutionalized (i.e. nursing homes, prisons, or chronic care facilities)
- 4. Not a transfer from a non-participating hospital, and
- 5. Presenting complaint of chest discomfort, with no obvious source of trauma, during initial evaluation in the ED of a participating hospital.

In addition to the above criteria, the primary population for the study will be those patients who are admitted to the hospital for possible acute ischemia and receive an ICD discharge code indicating a cardiac-related diagnosis. We will include all such patients irrespective of a previous history of MI. Since previous findings are consistent with the idea that patients with a history of CHD delay longer than those without such a history, we will examine this issue as an a priori subgroup hypothesis.

F. Primary Outcome

The primary specific aim of the study is to evaluate the effect of an 18 month community-wide intervention program on patient delay time from the onset of symptoms of acute IHD to arrival at the hospital in patients admitted for possible acute ischemic cardiac events who receive a cardiac-related diagnosis. This group is most readily identified as patients who are seen in the ED for chest pain, admitted with rule-out MI, unstable angina, or chest discomfort (or a synonym), and receive a cardiac-related discharge diagnosis (ICD 410-414, 427, 428, 429, 440, 786.5).

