Community contacts also serve as qualitative assessments designed to evaluate the resources and capacity of each organization to implement the proposed interventions. Discussions with key informants have yielded information regarding vested interest groups, informal networks, advocacy movements, potential community-specific barriers to intervention implementation and existing community organizations that may facilitate initiation of community activites. After baseline data are collected, contact with community leaders will be intensified in the intervention communities.

B. Characteristics of Study Communities

A number of community-specific variables were collected to assess variability across and comparability within pairs of communities. These variables include factors used to compare community sample distributions with the U.S. population and variables designated as matching criteria. In Section III., Table 1 provides variable categories and values applicable to each study community at a specific field site. The bottom of the table includes selected aggregate study percentages and comparable values based on 1990 U.S. Census statistics for comparison.

A few comments regarding figures tabulated in Table 1 simplify the interpretation of the data. Some field sites plan to combine two smaller communities to represent one study site. In this case, values shown in the table represent a weighted average of the two communities or individualized data is provided for each community. Finally, the numbers of expected emergency department visits for chest pain and discharges for myocardial infarction (ICD 410) and unstable angina (ICD 411) were estimated in some cases using data from the participating hospitals and, in other cases, using previously collected data from similar nearby communities.

VII. MEASUREMENT OF OUTCOME, PROCESS, AND IMPACT

A. Clinical Outcome Measurements

1. Primary outcome: primary definition of delay time

The primary outcome of delay time will be defined as the interval from symptom onset to arrival at the emergency department (ED) for patients admitted for possible acute cardiac ischemia and receiving a cardiac-related discharge diagnosis (ICD 410-414, 427, 428, 429, 440, 786.5). (The primary population)

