The available number of cases in each community is constrained by the local population and demographics as well as the pattern of hospital and emergencydepartment (ED) usage. Table 4 shows the projected number of cases in each community in three categories: total ED visits for chest pain; hospital discharges with ICD code 410 or 411; and confirmed cases of MI. Although the expected event rates in Table 4 come to 1202 per community for the 22-month trial, that rate is severely diminished by several mechanisms. First, a certain fraction of the patients discharged with 410/411 codes will present at the ED with complaints other than chest pain or will be admitted by some route not captured by the REACT sampling frame. Second, a certain fraction of cases will provide incomplete, invalid, or unusable data. Finally, a certain percentage of 410/411 diagnoses will fail to be validated. Early data showed that these mechanisms when compounded reduced the rate of usable cases by more than two-thirds, from 1202 to 375 per community. The REACT eligibility criteria were therefore revised to include all cardiac-related discharges. Broadening the criteria approximately doubled the expected sample, to 750 per community over 20 months, or a total of 15,000 usable cases.

The logistical demands of REACT measurement suggest, insofar as is compatible with sample-size requirements, that random subsampling of cases be conducted in the larger communities. Rather than lock the REACT design into a fixed subsampling scheme, the study will institute a conservative sampling plan that can be adjusted (without bias) as the data come in. In the smallest communities (two in the Washington field site and all four in the Texas site), 100% sampling will certainly be required throughout REACT. In the intermediate-sized communities, sampling will

begin at 100% but will be monitored by the Coordinating Center to determine whether "mid-course" adjustment to a smaller sampling fraction might be appropriate. In the largest communities (Worcester, MA and Eugene, OR), sampling will begin at 50% and will be similarly monitored and adjusted if necessary.

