REACT will follow the pattern employed in the analysis of the Minnesota Heart Health Program risk factor and morbidity and mortality data (97), and adapted for the joint analysis of data from the three major U.S. trials of community heart health promotion in the 1980's (71). Pre-intervention data from all 20 communities will be combined with postintervention data from the comparison communities to model a single secular trend. The intervention effect will then be estimated as a departure from that secular trend.

7. Subgroup analyses

Subgroup analyses are often desirable to provide insight into how and for whom an intervention achieved its effect. REACT plans a number of subgroup analyses, all secondary to the primary analyses. These include assessment of the treatment effect on delay among subgroups defined by sex, ethnicity/race, age, history of previous CHD, risk status, and other variables listed in Section IV. These analyses will be patterned after the primary analyses, with appropriate caution added to their interpretation.

8. Inferential parameters

All primary and secondary analyses will employ two-tailed tests with a nominal Type I error rate of 5%.

9. Intention to treat

A commonly followed principle in rigorously evaluated trials is the intention-totreat principle, which states that participants allocated to each condition must be retained in the primary analyses, even if that requires conservative procedures to estimate data for subjects lost to followup. REACT will be relatively protected in this regard, as it is not based on a cohort design and so will not be subject to the usual loss to followup problems. At the community level, the intention-to-treat principal implies that a community must be analyzed as belonging to the treatment condition to which it was randomized, regardless of how well the intervention was implemented (in the case of an intervention community) or how much the community may have been influenced by independent REACT-like messages (in the case of a control community).

B. Analytic Methods

1. Analysis of delay time in the primary population

The primary population for whom delay times in each community will be assessed consists of all patients with confirmed MI or unstable angina. This group will be referred to as *primary patients*. For the primary endpoint, delay time is defined to be the time between onset of symptoms and arrival at the hospital.

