- c. average peak CPK in primary patients in whom it is measured;
- d. number of patients dismissed to home from the ED after presenting with complaint of chest pain or discomfort ("false positives");
- e. number of patients discharged from the hospital with confirmed acute ischemic heart disease ("true positives").

For each continuous measurement *Y*, linear regression will be performed in each community. The dependent variable will be *Y*, and the independent variable will be calendar time. As with the primary analysis, the first six months of baseline values will be considered to have occurred at time 0. The 10 slope estimates for intervention communities will be compared to those of the control communities using a two-tailed paired *t*-test at α =0.05.

XII. PUBLICATIONS, PRESENTATIONS, AND ANCILLARY STUDIES POLICY

The REACT Study is an important scientific investigation impacting public education and health care. Because of the great effort that goes into such a study and the large amount of resources used, study investigators have the right and responsibility to communicate their findings to the scientific community and to the public at large.

To minimize the probability of inaccurate data in published materials, it is the policy of REACT that all data and text considered for all papers, and all abstracts for presentation at scientific meetings, be submitted to the Publications, Presentations and Ancillary Studies (PPAS) Committee for review and approval prior to presentation or publication. Also, the Coordinating Center shall review these materials to verify that they are accurate in nature and are consistent with data used in other REACT documents and papers. (Specific procedures to achieve this policy are delineated in Appendix B: REACT Publications, Presentations, and Ancillary Studies Procedures)

The objectives of the REACT PPAS policy are:

- 1. To assure and expedite orderly and timely presentations to the scientific community of all pertinent data resulting from the REACT study.
- 2. To assure scientifically accurate presentations and papers from REACT investigators.
- 3. To assure that all investigators, particularly those of junior rank, have the opportunity to participate and be recognized in the study-wide presentations and publications of REACT data.

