Many of the secondary questions in REACT concern the primary endpoint as measured in populations, smaller or larger, that differ from the primary group of patients with confirmed MI or acute ischemia presenting with chest pain. Smaller groups of interest include the two sexes; ethnic subpopulations; and MI patients alone. Larger groups include all patients presenting at the ED with chest pain.

Two distinct questions may be formulated with respect to a subgroup: (1) Did REACT Intervention have an effect in that subgroup, considered alone? (2) Did REACT Intervention have a different effect in that subgroup compared with the complementary subgroup?

To calculate detectable effects in answer to the first question, it is necessary merely to increase or decrease the overall sample sizes in the calculation for the primary endpoint, in proportion to the size of the group. This assumes that all design and variance parameters are unaffected by moving to a larger or smaller group; for example, that inter-pair slope correlation (ρ) is the same for women as for the primary sample as a whole.

v CISIOII U //U1/90

To calculate detectable effects for a comparison between two complementary subgroups, the fraction f of each community to be compared to the complementary fraction (1-f) will be assumed the same in each community, although this is clearly not true for certain subgrouping factors such as ethnicity. The 20 community-level endpoints become 40, as slope can be measured separately in each subgroup in each community. The contrast of interest is a second-order difference in each community pair:

$$d' = \begin{bmatrix} b_{Subgroup \#1, Intervention} - b_{Subgroup \#1, Control} \end{bmatrix} - \begin{bmatrix} b_{Subgroup \#2, Intervention} - b_{Subgroup \#2, Control} \end{bmatrix}$$

The average contrast over all 10 pairs, $\overline{d'}$, is an unbiased estimate of the differential effect of REACT Intervention by subgroup. Its variance is

$$SE^{2}(\overline{d'}) = V(\overline{d'}) = \frac{4\sigma_{\beta}^{2}}{J}(1-\rho-\dot{\rho}^{*})$$
$$+ \frac{\sigma^{2}}{V,J^{2}} \sum_{j=1}^{J} \left[(fK_{j})_{Intervention}^{-1} + (fK_{j})_{Control}^{-1} + ((1-f)K_{j})_{Intervention}^{-1} + ((1-f)K_{j})_{Control}^{-1} \right]$$

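### The analysis section, the framework and Appendix C still define the primary population as confirmed MI or unstable angina, although eligibility was broadened to all admitted patients with a cardiac-related discharge code

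*Protocol*

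**What the plan says.** The protocol's current text contains two definitions of the primary population.

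**Broad definition**
- I.B, primary aim: patients admitted for possible acute cardiac ischemia "and receiving a cardiac-related discharge diagnosis".
- IV.E: "the primary population for the study will be those patients who are admitted to the hospital for possible acute ischemia", with an ICD code for a cardiac-related diagnosis. IV.F lists the codes and gives four reasons for choosing this group.
- VII.A.1: delay time is measured "for patients admitted for possible acute cardiac ischemia and receiving a cardiac-related discharge diagnosis (ICD 410-414, 427, 428, 429, 440, 786.5", and the text labels this group as the primary population.
- X.A: after early data showed too few usable validated 410/411 cases, "The REACT eligibility criteria were therefore revised to include all cardiac-related discharges".

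**Narrow definition**
- XI.B.1: "The primary population for whom delay times in each community will be assessed consists of all patients with confirmed MI or unstable angina". The section names this group primary patients and then sets out the model and the paired t-test.
- XI.B.1, after model (1): the study patients are treated as a random sample of a community's potential MI patients.
- I.D: the primary outcome is delay time "in patients with confirmed acute cardiac ischemia (validated AMI or unstable angina".
- Appendix C, section C: "the primary group of patients with confirmed MI or acute ischemia presenting with chest pain".
- Table 8: a half 410, half 411 case mix for the primary population, with validation rates for each code.

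XI.B.5 uses primary patients as the denominator for several secondary endpoints, for example "average peak CPK in primary patients in whom it is measured". IV.G.3 sets early revascularization in ICD 410/411, infarct severity in ICD 410, and case fatality in patients with cardiac diagnoses.

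**The concern.** XI.B.1 is where an analyst looks to see who enters the primary test, and Appendix D gives the Section XI analyses first priority and makes them the basis of the principal publications. A superseded definition there is therefore more serious than one in a background section.

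The two populations can give different answers to the primary question. The broad one adds discharges coded 412-414, 427, 428, 429, 440 and 786.5 and needs no validation of the diagnosis. The data allow either group to be formed, so an unresolved wording leaves room to choose after results are seen.

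The narrow reading also breaks a planned analysis. IV.G.1.d compares AMI, unstable angina and other cardiac diagnoses, and the third category cannot exist in a population limited to the first two.

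Correcting XI.B.1 alone has a side effect. Peak CPK and reperfusion would then be summarised in all cardiac-coded admissions, contrary to IV.G.3.

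**Working it through.** **Inputs**
- J = 10 pairs, t with 9 df, two-sided 5%, 80% power (X.B).
- L = 1.5 yr, B = 0.333 yr, V_t = 459/1936 = 0.237 yr² (Appendix C, section B).
- R = 9, so σ = 0.5·log10(9) = 0.477.
- R_β = 1.05 or 1.15, with σ_β = log10(R_β)/(2L); ρ = 0, 0.2 or 0.4 (Appendix C, Table 8).
- Usable cases per community: 375 before broadening, 750 after (X.A); planning case 600 (X.C).

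**Formula, with equal K in all communities**

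SE² = 2σ_β²(1−ρ)/J + 2σ²/(K·V_t·J)

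Detectable Δβ = SE·(2.262 + 0.883); relative reduction = 1 − 10^(−L·Δβ); minutes = relative reduction × 150 or 180.

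**Reproducing the plan (K=600, R_β=1.05, ρ=0.4)**

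The slope term is 2(0.00706)²(0.6)/10 = 0.0000060. The sampling term is 2(0.2276)/(600 × 0.2371 × 10) = 0.000320. SE = 0.01806, Δβ = 0.0568, and the reduction is 1 − 10^(−0.0852) = 17.8%. Table 5 gives 18%. The K = 800 and K = 400 rows also reproduce to rounding.

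**Results (range from R_β=1.05, ρ=0.4 to R_β=1.15, ρ=0)**

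| K | Relative | M = 2.5 h | M = 3 h |
|---|---|---|---|
| 750 (broad, expected) | 16.1-18.1% | 24-27 min | 29-33 min |
| 600 (planning case) | 17.8-19.6% | 27-29 min | 32-35 min |
| 400 (pessimistic row) | 21.3-22.7% | 32-34 min | 38-41 min |
| 375 (narrow) | 21.9-23.3% | 33-35 min | 39-42 min |

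At K = 375 and M = 3 h, R_β = 1.05 gives 39.4-39.6 min and R_β = 1.15 gives 40.8-41.9 min. Only the latter passes 40 min.

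**Power for a 30 min reduction (noncentral t)**
- M = 2.5 h: 88-94% at K = 750, 82-89% at 600, 66-72% at 375.
- M = 3 h: 73-83% at K = 750, 65-74% at 600, 49-54% at 375.

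For a 40 min reduction, K = 375 gives 91-94% (M = 2.5 h) and 76-81% (M = 3 h).

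**Case ratios**

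375/750 = 0.50 and 375/600 = 0.625. The 375 derives from a 22-month count (1202) and the 750 is stated over 20 months, so the first ratio is approximate.

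**How far the comparison depends on R = 9**

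Only the sampling term, proportional to (log10 R)²/K, differs between the groups. With R = 9 in the broad group, a test on 375 narrow cases matches K = 600 if log10 R = √0.625 × 0.954 = 0.754, that is R ≈ 5.7. It matches K = 750 if log10 R = √0.5 × 0.954 = 0.675, that is R ≈ 4.7.

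**Table 8**

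Its attrition entries applied to 1202 give 1202 × 0.85 × 0.85 × (0.5 × 0.90 + 0.5 × 0.60) = 651, or 738 with the 80% validation rate. These are narrow-group figures that the early data in X.A overtook.

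**The case against.** The strongest reply is that the intended population is not in doubt. X.A says the criteria were revised and why, IV.E-F states and justifies the broad group, and VII.A.1 labels it. A reader might infer from the conflict that nothing says which definition governs. The documents do not support that: these sections point one way, and the narrow text is an incomplete revision. What stands is that the section specifying the test was among those left unrevised.

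A reader might also infer that XI.B.1 discards half the sample on which the power statement rests. It does not. The planning case in X.C is 600 per community, so the narrow group is 62.5% of it. The half applies only against the expected 750.

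Nor does the narrow reading leave the trial without useful power. Table 5 already discloses 400 cases, and 375 is only about 1 min worse. Most of the K = 375 range lies inside the 30-40 min target.

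The comparison also uses one residual spread for both groups. R = 9 is drawn from the Section II literature, which is mainly about AMI, and no figure shows that it holds in each group.

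Finally, the XI.B.5 mismatch is not uniform. In-hospital death among primary patients is right under the broad definition, as IV.G.3.c and VII.A.3.c show.

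**Conclusion.** The contradiction stands, in current text and on the definition of who enters the primary test. XI.B.1, I.D, Appendix C section C and Table 8 carry the superseded population. I.B, IV.E-F, VII.A.1 and X.A carry the intended one.

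Followed literally, XI.B.1 would cut the expected usable cases per community from about 750 to about 375. The detectable reduction would be about 6 min larger at a 2.5 h median, and about 7 min larger at 3 h, than in the K = 600 planning case. This rests on equal K across communities, on R = 9 in both groups, and on the approximate 375 and 750.

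The power loss is material but secondary. The change is needed because the primary population should have one definition, stated where the test is specified. For XI.B.5, the conflict with IV.G.3 is limited to reperfusion, peak CPK and, as a severity measure, ventricular fibrillation.

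**What to change.** 1. In XI.B.1, I.D and Appendix C section C, replace the narrow definition with that of IV.F/VII.A.1, including the ICD list.
2. In XI.B.1, reword the sentence after model (1) so that the sampled population is the broad one, not potential MI patients.
3. In Table 8, update the case mix and replace or remove the 410/411 validation rates, so that the entries agree with the revised count in X.A.
4. Keep confirmed MI/unstable angina as a named secondary population, analysed by the same method.
5. In XI.B.5, use ICD 410/411 for reperfusion (IV.G.3.a) and ICD 410 for peak CPK (IV.G.3.b). Use ICD 410 for ventricular fibrillation too, since VII.A.3.b counts ventricular arrhythmias as severity. Leave in-hospital death on the broad primary population.

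Most of this is wording, and no new data collection is needed. Table 8 is the exception: its revised entries must come from the early data behind X.A, which the protocol does not tabulate. The revision should be made before outcome data are compared by group.
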